Induction of labor is necessary in one-fourth of women and a large proportion require cervical ripening. Cervical ripening is necessary to shorten the time to delivery and increases the chances of a vaginal delivery. The superior method for cervical ripening has long been debated. The two techniques utilized are mechanical and pharmacological methods. Pharmacological techniques center on formulations of prostaglandin but are associated with higher risks of tachysystole compared to mechanical methods. The primary mechanical method used is a transcervical Foley catheter with the balloon filled with 30-80 mL of sterile fluid. Downward tension on the internal os by the filled balloon leads to production of endogenous prostaglandins leading to remodeling of the cervix. A Cochrane review has shown similar efficacy between pharmacological and mechanical methods, but both were found to be superior to oxytocin for cervical ripening.

There has only been one randomized controlled study evaluating the transcervical Foley catheter for cervical ripening in the outpatient setting. The primary outcome of this study was a change in the Bishop score between the groups, and it found the Bishop scores were similar between the two groups. While not powered to detect a difference, it did show women in the outpatient group spent less time in the hospital without any adverse events. Outpatient cervical ripening is an attractive alternative to women and physicians because of the decreased amount of time spent in the hospital and opportunity for patients to be in the comforts of their home; however, few have adopted this method since there is only one study evaluating outpatient cervical ripening with a transcervical Foley catheter. The safety of the transcervical Foley catheter has been well-established, though, and it is not associated with increased risks of adverse events such as chorioamnionitis, endometritis, placental abruption, or stillbirth.

We will conduct a randomized controlled trial comparing outpatient to inpatient cervical ripening using a transcervical Foley catheter. The primary outcome is the time from admission to delivery. We hypothesize that women in the outpatient group will have shorter durations from admission to delivery than the standard inpatient cervical ripening group. We also predict the outpatient patients will have a higher satisfaction than the inpatient group because of the opportunity to be in their own home during the ripening period. Women will be randomized to undergo inpatient or outpatient transcervical Foley catheter cervical ripening beyond their 39th week of gestation. Women and their infants will be followed until the time of their discharge.

1.1 Primary Hypothesis

Patients in the outpatient transcervical Foley catheter group will have a shorter time interval from admission to delivery than the inpatient group.

1.2 Secondary Hypotheses

- a. Patients in the outpatient group will have higher satisfaction scores than those undergoing cervical ripening in the inpatient setting.
- b. The following hypotheses pertain to the incidence of the following events:
 - a. Outpatient cervical ripening will not increase the incidence of adverse outcomes compared to inpatient cervical ripening. Based on prior studies evaluating the safety of the transcervical Foley catheter, we do not anticipate there to be heavy vaginal bleeding, immediate need for delivery for a non-reassuring fetal heart tracing, or stillbirths in either group.
 - b. A small number of patients in the outpatient transcervical Foley catheter group will require admission prior to their scheduled arrival time because of intractable pain from the transcervical Foley catheter. Additionally, a small number of patients will require an epidural for pain control while the Foley catheter remains in situ.
 - c. Immediate delivery for non-reassuring fetal heart rate tracings after placement of the transcervical Foley catheter will not be required in either group.
 - d. A small number of patients in the outpatient transcervical Foley catheter group will present to the Maternity Evaluation Unit (MEU) for evaluation prior to their scheduled admission time.
 - e. Spontaneous rupture of membranes (SROM) will occur at similar rates in the two groups.
 - f. Outpatient cervical ripening with the Foley catheter will not increase infectious morbidity as compared to inpatient cervical ripening.
- c. Epidural usage, and thus immobilization, will be higher in the inpatient group compared to the outpatient group.
- d. The outpatient and inpatient groups will have similar rates of vaginal and cesarean deliveries.
- e. The following hypotheses pertain to oxytocin usage between the two groups:
 - a. The inpatient group will require longer duration of oxytocin infusion, higher cumulative doses, and higher maximum rates than the outpatient transcervical Foley catheter group.
- f. The outpatient group will have lower labor and delivery charges than the inpatient group.
- g. Outpatient cervical ripening will not increase the risk of adverse neonatal outcomes compared to inpatient cervical ripening, as assessed by a composite neonatal outcome. This composite neonatal outcome measure will include Apgar score < 7 at 5 minutes, arterial cord blood gas pH < 7.1, arterial cord blood gas base deficit or excess < -12, and/or admission to the neonatal intensive care unit.

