5.1 Sample Size for Primary Outcome

Assuming an alpha of 0.05 with an 80% power and a standard deviation of 24 hours, 64 patients will be needed in each group to detect a 12 hour difference in means between the groups.

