5.3. Analysis Plan

Standard baseline characteristics between the two groups will be collected at baseline. It is assumed that randomization will evenly distribute baseline characteristic differences between the two groups, and thus, we do not anticipate adjusting for these in the primary analysis. Secondary analyses will, though, be analyzed using regression adjustments to account for any possible confounding covariates between the two groups. The primary analysis will be done in an intent-to-treat basis.

The primary analysis will compare the total admission to delivery time in minutes between the two groups. This will be analyzed using a two-sided student's t-test.

5.4. Secondary Aims:

The secondary analyses will be to compare the incidence of certain events between the two groups. A Chi-square p-value, relative risk, and 95% confidence interval will be calculated.

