5.5. Interim Monitoring

We propose an interim analysis when 32 patients in each group have completed the study (50% completion) to determine whether continuation of the study is necessary. We do not propose a formal stopping rule for safety, but the DSMB will continually monitor the study for safety.

6. Future studies

If our results show outpatient transcervical Foley catheter placement is safe, well-tolerated, and reduces hospital admission time to delivery, we will submit a Patient Centered Outcomes Research Institute (PCORI) grant to conduct a multi-center trial in an attempt to alter current induction methods and ultimately improve patient satisfaction and outcomes.

7. References

- 1) World Health Organization: WHO recommendations for induction of labour, Department of reproductive health and research. Geneva, Switzerland: World Health Organization; 2011:32.
- 3) Wing DA. Labor induction with misoprostol. *Am J Obstet Gynecol* 1999 Aug;181(2):339-45.

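### The hypotheses of no increase in harm have no criterion beyond a chi-square for a difference, and with 64 per arm a non-significant result cannot support them

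*Combined protocol and SAP*

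**What the plan says.** Section 1.2 contains three hypotheses that deny an increase in harm:

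- item b.a: "Outpatient cervical ripening will not increase the incidence of adverse outcomes compared to inpatient cervical ripening";
- item b.f: "Outpatient cervical ripening with the Foley catheter will not increase infectious morbidity as compared to inpatient cervical ripening";
- item g: "Outpatient cervical ripening will not increase the risk of adverse neonatal outcomes compared to inpatient cervical ripening".

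None has a margin or an acceptable upper limit. For the incidence of events, section 5.4 says: "A Chi-square p-value, relative risk, and 95% confidence interval will be calculated". It does not give the level or sidedness of the chi-square, or say which of the three results decides a hypothesis. Section 5.2 admits limited power for small differences in the secondary outcomes other than satisfaction.

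Section 6 makes the next grant application conditional on a finding that begins: "If our results show outpatient transcervical Foley catheter placement is safe, well-tolerated". It does not define how safety would be judged. Section 5.5 has no formal stopping rule for safety and leaves continuing oversight to the DSMB.

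**The concern.** A chi-square of this kind takes equal risks as its null hypothesis. Rejecting it shows a difference. Failing to reject it shows only that the data did not exclude equality, which in a small trial is the usual result whether or not risk has risen. A hypothesis of no increase needs the reverse: data that exclude an increase large enough to matter. That is read from the upper confidence limit, not from the p-value.

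The plan names the hypotheses and the test but does not link them, and the sample size was set for a different outcome. At stake is the safety statement that section 6 makes one of the conditions for a multi-center trial.

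**Working it through.** **Inputs.** From section 5.1: "Assuming an alpha of 0.05 with an 80% power and a standard deviation of 24 hours, 64 patients will be needed in each group". The effect sought there is a mean difference of 12 hours. Section 5.3 makes the primary test two-sided. The documents give no inpatient rates for infection or the neonatal composite, so a range is used. A two-sided 5% level is assumed for the chi-square. A doubling of risk is used as a benchmark only, since the plan sets no margin.

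**1. The plan's own figure.** n = 2 × [24 × (1.960 + 0.842) / 12]² = 2 × 5.604² = 62.8, so 63 per arm by the normal approximation. The t-test calculation gives 63.77, so 64, with power 80.1%. The stated 64 is reproduced, and it concerns time to delivery only.

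**2. Power of the chi-square to detect a true doubling, 64 per arm.** The approximation is Φ[(d − 1.96 × se0) / se1], where d is the difference in risk, se0 = √[2p̄(1 − p̄)/64] and se1 = √{[p1(1 − p1) + p2(1 − p2)]/64}.

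- 5% to 10%: se0 = 0.0466, se1 = 0.0464; (0.05 − 0.0913)/0.0464 = −0.89, giving 18.7%.
- 10% to 20%: se0 = 0.0631, se1 = 0.0625; (0.10 − 0.1237)/0.0625 = −0.38, giving 35.2%.

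Exact enumeration of the two binomials, without continuity correction, gives:

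| Inpatient rate (assumed) | Outpatient rate | Power | Doubling not significant |
|---|---|---|---|
| 1% | 2% | 2% | 98% |
| 2% | 4% | 8% | 92% |
| 5% | 10% | 19% | 81% |
| 10% | 20% | 35% | 65% |
| 15% | 30% | 53% | 47% |
| 20% | 40% | 71% | 29% |
| 25% | 50% | 85% | 15% |

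Power passes 50% at an inpatient rate of about 14% and 80% at about 23%. At the rate in section 2.4 for cesarean for a non-reassuring tracing in the theoretical outpatient period (3/1905 = 0.16%), power is essentially nil.

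**3. What particular results would leave open.**

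- 6/64 v 6/64: the standard error of the log relative risk is √[2(1/6 − 1/64)] = 0.550. The interval is exp(±1.96 × 0.550) = 0.34 to 2.9. For the risk difference, the Wilson limits of 9.4% are 4.4% and 19.0%, so Newcombe's half-width is √(9.61² + 5.01²) = 10.8 percentage points.
- 3/64 v 3/64: the standard error is √[2(1/3 − 1/64)] = 0.797, so the relative risk interval is 0.21 to 4.8.
- Inpatient 6/64 v outpatient 12/64: relative risk 2.0, standard error √(1/6 + 1/12 − 2/64) = 0.468, interval 0.80 to 5.0, chi-square p = 0.13. An observed doubling would not be significant.
- 0/64 in one arm: the exact two-sided 95% upper limit is 1 − 0.025^(1/64) = 5.6%.

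**4. Could this trial exclude a doubling formally?** With equal true rates p, one-sided 0.025, 80% power and an absolute margin equal to p, n = 2p(1 − p) × 7.849 / p². That is 299 per arm at 5%, 142 at 10% and 63 at 20%. Unless events are common, 64 per arm is too few, so estimation is the realistic aim.

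**The case against.** A reader might infer that the investigators will declare outpatient ripening safe whenever the p-value exceeds 0.05, and would do so in most trials in which risk had doubled. The documents do not support that. No section says non-significance will be read as safety, and section 6 leaves the basis for that finding open. The share of trials missing a doubling depends on rates the documents do not give. It exceeds half only below an inpatient rate of about 14%, and at 25% the test would detect a doubling in 85% of trials.

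Other points also stand:

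- The relative risk and its interval are already planned, and a report of 2.0 (0.80 to 5.0) would show the uncertainty plainly.
- Section 5.2 concedes limited power.
- These are secondary hypotheses. Section 6 concerns a grant for a larger trial, not adoption of the practice, and the DSMB watches safety throughout.
- Several items in section 4.8.2 (c, e, g and h) are defined in the outpatient group only, so no between-arm test applies.
- Section 1.2 expects no heavy bleeding, immediate delivery for a non-reassuring tracing or stillbirth in either group. With no events in both arms the chi-square cannot be computed.

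None of this supplies the missing criterion. The interval is planned, but nothing makes it decisive. The concession in section 5.2 covers small differences, and a doubling is not small. With no inpatient events the relative risk is undefined.

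**Conclusion.** The concern holds as a missing link between hypothesis and analysis. The plan claims no increase in adverse outcomes, infectious morbidity and the neonatal composite, names only a test of difference, and gives no criterion for safety. With 64 per arm a non-significant chi-square cannot support those claims. Power for a doubling runs from 19% at an inpatient rate of 5% to 85% at 25%, and equal counts of six still leave room for an increase of 10.8 percentage points. These figures assume the stated control rates, a two-sided 5% level, no continuity correction (which would lower power) and all 64 per arm analysed.

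The point is confined to outcomes compared between arms. It does not touch the primary analysis, and it does not show that the investigators intend to misread a null result.

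**What to change.** - **Section 5.4.** For safety outcomes measured in both arms, base the conclusion on the 95% confidence interval of the risk difference, outpatient minus inpatient, alongside the planned relative risk. Report the upper limit as the largest increase not ruled out. Use a score-based interval such as Newcombe's, which stays computable with zero events: 0/64 v 0/64 gives ±5.7 points, from a Wilson limit of 3.84/(64 + 3.84). State that a non-significant p-value will not be taken as evidence of no increase.
- **Section 5.4, outpatient-only items.** Report proportions with exact intervals.
- **Section 1.2.** Present items b.a, b.f and g as aims to estimate the difference in risk, not as hypotheses to be tested.
- **Section 6.** Replace the unqualified reference to safety with a statement conditional on those upper limits.

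This changes wording and one interval calculation, with no extra patients or data. The cost is a less favourable safety conclusion: the report will have to name increases that the trial could not exclude.

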1.3 Purpose of the Study Protocol

The purpose of this study is to determine whether outpatient cervical ripening with a transcervical Foley catheter in multiparous women shortens the total time in labor and delivery from the time of admission to the time of delivery compared to women who undergo cervical ripening in the standard inpatient fashion. This protocol describes the rationale, design, and organization of this randomized control study.

2. Background

2.1 Introduction

In developed countries, approximately 20-25% of pregnant women undergo an induction of labor [WHO 2011, Kelly 2013]. Fifteen percent of these women will require cervical ripening [Wing 1999]; in the setting of an unfavorable cervix, oxytocin alone can lead to longer times to delivery, tachysystole, and increased rates of cesarean delivery [Alfirevic 2009]. Methods for cervical ripening can be pharmacologic or mechanical. A Cochrane review demonstrated that mechanical methods of cervical ripening were equivalent to prostaglandin and superior to oxytocin administration [Jozwiak 2012]; furthermore, mechanical methods were safer, with decreased rates of adverse outcomes such as hyperstimulation [Jozwiak 2012].

Given rising medical costs and the length of the latent phase of labor, the concept of outpatient cervical ripening is attractive to both practitioners and patients [Farmer 1996]. Studies have shown outpatient induction is feasible and safe. The majority of the studies have evaluated outpatient induction of labor using prostaglandin E2 [Dowswell 2010, O'Brien 1995, McKenna 1999]. One of the greatest fears of outpatient induction of labor is nonreassuring fetal heart tracings. The lower risk of hyperstimulation associated with mechanical methods makes Foley catheter induction of labors particularly more attractive for use in the outpatient setting. Sciscione et al [Sciscione 2001] published the first randomized controlled trial comparing outpatient transcervical Foley catheter induction of labor to standard inpatient management. They demonstrated a decreased length of stay of 9.6 hours in the outpatient group without any adverse maternal or neonatal outcomes in the outpatient group [Sciscione 2001]. This study led the American College of Obstetricians and Gynecologists (ACOG) to make the profound statement regarding outpatient Foley catheters for induction of labor, "mechanical methods may be particularly appropriate in the outpatient setting. [ACOG 2009]" However, few obstetricians have incorporated this endorsement from ACOG.

In our institution, cervical ripening is exclusively performed using a transcervical 16 French Foley catheter with 30mL of sterile saline. This method has been proven to shorten the time to delivery compared to the PGE2 vaginal insert without increasing the cesarean delivery rate [Edwards 2014]. Additionally, Pettker et al [Pettker 2008] demonstrated there was not benefit to adding oxytocin to the transcervical Foley catheter induction method. Patients requiring cervical ripening spend a considerable amount of time in the latent phase. This prolonged period of time represents a significant portion of patients' intrapartum hospital costs. Additionally, while patients are not confined to bed, many patients choose to immobilize themselves during this period. As such, our objective is to evaluate the feasibility, safety, patient satisfaction, and cost associated with outpatient as compared to inpatient induction of labor with Foley catheterization for cervical ripening in low-risk women in a single academic institution in the southern United States. Contrary to Sciscione et al's [Sciscione 2001] study where the primary outcome was change in Bishop score, our study will be powered to detect a 12 hour reduction in time from admission to delivery.

2.2 Current recommendations for cervical ripening

Cervical ripening is necessary when the cervix is not softened and thinned, which are normal architectural remodeling processes the body goes through in preparation for labor. The most commonly used mechanical dilating method in the United States is the transcervical Foley catheter balloon. In this technique, a sterile urological 14-26 French catheter is inserted through the cervix, and then the tip is inflated with 30-80 mL of fluid. This downward pressure of the tip of the catheter cause endogenous prostaglandins to be released which potentiates the remodeling process required for cervical ripening.

2.3 Prior studies on outpatient induction of labor

There has only been one randomized controlled trial investigating the outpatient use of a transcervical Foley catheter for cervical ripening. Sciscione et al (2001) included 111 women in their trial (n = 61 inpatient and n = 50 outpatient), and their primary outcome was a change in the Bishop score. The Bishop score was recorded at placement of the transcervical catheter and then again when the catheter extruded or when the outpatient group presented for induction of labor. There was not a difference in Bishop scores between the two groups. There were not any adverse events in the outpatient group, and the outpatient group spent nearly 10 hours less in the hospital than the inpatient group. Other studies investigating outpatient cervical ripening have focused on prostaglandins, which increased the rates of tachysystole, but did not increase maternal or neonatal morbidity or mortality.

2.4 Safety of outpatient induction of labor

There is limited data on outpatient cervical ripening, and thus, this prompted authors of a Cochrane review (Kelly et al 2013) to conclude there was not sufficient evidence to establish the safety of cervical ripening in the outpatient setting. Sciscione et al (2014) created a theoretical cohort of outpatient transcervical Foley catheter for cervical ripening and reviewed labor and delivery as well as neonatal outcomes in over 1900 women. This "low-risk" cohort excluded patients with gestational hypertension, preeclampsia, multiple gestations, pregestational diabetes, and stillbirth, and found no adverse events in the group. There were not any cases of placental abruption or stillbirths. Only 2/1905 had an emergent cesarean section after placement of the transcervical Foley catheter for non-reassuring fetal heart rate tracings during the immediate postplacement monitoring. Only 3/1905 required a cesarean section for non-reassuring fetal heart rate tracings during the theoretical "outpatient" time period.

We have reviewed 43 consecutive privately insured cervical ripening admissions at the University of Alabama at Birmingham. In this cohort, transcervical Foley catheters were placed without initiation of oxytocin. There were not any placental abruptions, non-reassuring fetal heart rate tracings necessitating delivery, or stillbirths between placement of the transcervical Foley catheter and the next morning, which represented a theoretical "outpatient" time period.

2.5 Rationale for a clinical trial

While the American College of Obstetricians and Gynecologists (ACOG) stated in the Practice Bulletin Induction of Labor, “mechanical methods may be particularly appropriate in the outpatient setting,” few obstetricians practice outpatient cervical ripening because of only one randomized controlled trial investigating this method.

2.6 Innovation

There is a critical need for further studies to establish the safety, efficacy, and patient satisfaction of transcervical Foley catheter for cervical ripening in the outpatient setting. The only study investigating outpatient transcervical Foley catheter conducted to date was powered to detect a change in the Bishop score between the two groups and not total inpatient time. Our study will be the first randomized controlled trial powered to detect a difference in admission to delivery time between the two groups.

3. Study Design

This is a randomized controlled trial comparing time from admission to delivery in outpatient versus inpatient groups undergoing transcervical Foley catheter placement for cervical ripening.

